Protocol:

Jowl Improvement with Injectable Fillers: Jaw line Injections alone vs Jawline and Cheek Injections

NCT04389866

Document date 04/24/2020

Jowl Improvement with Injectable Fillers: Jawline Injections alone vs Jawline and Cheek Injections [name] [name]

Clinical Investigation Plan

Date: 04/24/2020

Protocol number: 10001

Version: 4

Investigator:

[name] [name] Advanced Dermatology [name]

[contact] [contact] Sponsor:

Advanced Dermatology [name] [contact]

[contact]

Funded By: Allergan

Introduction

This is a prospective clinical study to demonstrate a reduction in jowling and laxity of the jawline that can be achieved following facial volume enhancement using JUVÉDERM VOLUMA™ XC. The secondary measure

will be if this can be achieved with jawline injection only, or if a superior result can be obtained with both cheek and jowl injection.

Present methods for treating jowling include:

- 1. Temporary, semi-permanent and permanent injectable filler substances
- 2. Tissue tightening devices and radiofrequency microneedling
- 3. Suture lifts
- 4. Surgical implants
- 5. Surgical face lifts

Early experimentation by the author with volume replacement using JUVÉDERM VOLUMA® XC has yielded good results with an excellent safety profile and minimal downtime or adverse events. This study was undertaken to determine if patient satisfaction and results can be measured by a reduction in jowl laxity and jawline crispness with apparent lift and whether it is enough to treat the jawline alone or it is best to treat the jawline in conjunction with the cheeks.

Study Rationale

Hyaluronic acid fillers are used primarily for the reduction of wrinkles and age-related volume deficits. A common complaint of women is the formation of jowls, and they frequently pull up their skin toward their ears to indicate an outcome they wish for. In the past, face lift was the principle method to treat this problem, but many newer less-invasive techniques attempt to improve this area. One treatment that is a few years old is the dissolvable suture lift, targeting the mid cheek and jawline to lift the face. Another newer technique is the radiofrequency needling technique. Older treatments include skin tightening treatments with radiofrequency or focused ultrasound.

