This study proposes to evaluate a new indication for JUVÉDERM VOLUMA™ XC, for which the benefit/risk profile has not been entirely assessed. While the risks of stroke and blindness may be small, the jawline and cheek are highly vascularized areas. Due to limited experience and research associated with dermal filler use in this area, the actual risk is unknown.

Alternatives

Alternatives to treatment include but are not limited to other injectable fillers, surgical implants, and surgery.

Study Purpose and Objectives

Purpose:

The purpose of this clinical investigation is to study the perceived reduction of jowling following a volume replacement treatment using JUVÉDERM VOLUMA™ XC in the jawline or in the jawline and the cheek

Primary Objective:

The primary objective of this study is to see that a clinically relevant jowl improvement can be achieved with hyaluronic acid filler into the jawline and/or cheek (Endpoint #1).

The secondary objective is to determine which of the 2 methods (jowl injection alone or jowl injection with cheek injection) is superior (Endpoint #2).

Study Design

Scope:

The clinical study will include 16 patients at one clinical site.

Duration:

Eligible patients will receive 1 treatment according to the study protocol, and will be followed for a period of 12 months to document safety and efficacy. Patient and/or doctor may choose to have a touchup at 1 month. All subjects will be followed for 12 months from the time of the last injection session.

Patient Selection

Each patient will be evaluated by the Investigator to assess his or her suitability for entry into the study.

- 1. Jowling grade 2-3 by the Lower Face Jawline at Rest Scale (1), by both MD evaluator and patient.
- 2. Female patients must not be pregnant or trying to get pregnant and must have negative urine pregnancy tests before treatment.
- 3. Non-pregnant females ages 35-65 in good general health.
- 4. A study participant must be able to give proper informed consent in writing and be willing to follow the treatment schedule and undertake to carry out all necessary precautions and instructions.
- 5. Able to participate in telemedicine video visits.
- 6. Able to understand the requirements of the study and willing and able to follow all study procedures and attend all study visits, and successfully complete the study.

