Photographs will remain unretouched. One blinded dermatologist and one unblinded dermatologist will rate the patient's severity of jowling based on the Jawline Rating Scale (JRS) (1) at baseline, the 4-week, 8-week, and 12 or 16-week visits. The patient will also rate their jowling based on the JRS as well as their satisfaction with the procedure.

Analysis of Scientific Soundness of the Protocol

The proposed study has been designed to provide a valid method to analyze the safety and efficacy of facial volume replacement. Measure taken to assure that the study provides valid data are as follows:

- 1. Photographs will be taken under standardized conditions. Photographs will be taken with a VISIA CR, a device made by Canfield Scientific specifically to be utilized for clinical research to provide uniformity in patient photographs.
- 2. Adverse or unanticipated effects that occur during the course of this clinical study will be recorded and carefully analyzed as to their relationship to the treatment.
- 3. Evaluators will review individual photos without knowledge of if they are before or after photos.

Primary Outcome Measure:

The primary outcome is a reduction of 1 or more points of the Jawline Rating Scale (JRS)
 Assessment (on scale of 0 to 4) at baseline versus that at 4 weeks from the last injection (whether initial or touch-up) based on any or all of one blinded dermatologist rating, one unblinded dermatologist rating, and patient rating. (A lower number will mean a better outcome) Time Frame: Baseline to 4 weeks after last injection.

Secondary Outcome Measures

- 1. Reduction of 1 or more points of the Jawline Rating Scale (JRS) Assessment (on scale of 0 to 4) at baseline versus that at 4 weeks from the last injection based on the patients rating while looking in the mirror and at before and after photographs. A lower number will mean a better outcome. Time Frame: 4 weeks from last injection
- 2. Whether group 1 and group 2 has a higher reduction in the Jawline Rating Scale (JRS) (on scale of 0 to 4) at 4 weeks from the lastinjection compared to baseline based on ratings from one blinded dermatologist and one unblinded dermatologist. A lower number will mean a better outcome. Time Frame: 4 weeks from last injection

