- 3. Whether group 1 or group 2 has a higher reduction in the Jawline Rating Scale (JRS) (on scale of 0 to 4) at 4 weeks from the last injection compared to baseline based on the patients rating while looking in the mirror and at before and after photographs. A lower number will mean a better outcome. Time Frame: 4 weeks from last injection
- 4. Jawline Rating Scale (JRS) Assessment on scale of 0 to 4 at 4 weeks: One blinded dermatologist and one unblinded dermatologist will rate the patient's severity of jowling based on the Jawline Rating Scale (JRS). The patient will also rate their jowling based on the Jawline Rating Scale (JRS). The scale is on a rating of 0 to 4. A lower number will mean a better outcome. [Time Frame: 4 weeks]
- 5. Jawline Rating Scale (JRS) Assessment on scale of 0 to 4 at 8 weeks: One blinded dermatologist and one unblinded dermatologist will rate the patient's severity of jowling based on the Jawline Rating Scale (JRS). The patient will also rate their jowling based on the Jawline Rating Scale (JRS). The scale is on a rating of 0 to 4. A lower number will mean a better outcome. [Time Frame: 8 weeks]
- 6. Jawline Rating Scale (JRS) Assessment on scale of 0 to 4 at 12 or 16 weeks: One blinded dermatologist and one unblinded dermatologist will rate the patient's severity of jowling based on the Jawline Rating Scale (JRS). The patient will also rate their jowling based on the Jawline Rating Scale (JRS). The scale is on a rating of 0 to 4. A lower number will mean a better outcome. [Time Frame: 3 months from last treatment]
- Incidence of abnormal eye exam (Confrontational Visual Fields Exam) findings (Safety):
 Ophthalmologic exams that include Confrontational Visual Fields Exam will be performed prior to any
 treatment, 30 minutes after treatment, and at all follow up in-person visits. [Time Frame: up to 18
 months]
- 8. Incidence of abnormal eye exam (Snellen Eye Exam) findings (Safety):
 Ophthalmologic exams that include Snellen Eye Exam will be performed prior to any treatment, 30 minutes after treatment, and at all follow up in-person visits. [Time Frame: up to 18 months]
- 9. Incidence of abnormal eye exam (Ocular Motility Exam) findings (Safety):
 Ophthalmologic exams that include Ocular Motility Exam will be performed prior to any treatment,
 30 minutes after treatment, and at all follow up in-person visits. [Time Frame: up to 18 months]

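### The plan asks whether treating the jawline alone is enough, but no stated outcome gives the responder proportion in Group 1

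*Combined protocol and SAP*

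**What the plan says.** **The question.** The Introduction says the study was undertaken to find out, among other things, "whether it is enough to treat the jawline alone or it is best to treat the jawline in conjunction with the cheeks". It describes the secondary measure in similar terms: it "will be if this can be achieved with jawline injection only, or if a superior result can be obtained" by treating both areas.

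**The objectives.** Under Study Purpose and Objectives, the primary objective is that "a clinically relevant jowl improvement can be achieved with hyaluronic acid filler into the jawline and/or cheek (Endpoint #1". The next sentence reads "The secondary objective is to determine which of the 2 methods (jowl injection alone or jowl injection with cheek injection) is superior (Endpoint #2". The Purpose statement just above describes the two regimens as they are actually given: jawline, or jawline together with cheek.

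**The outcomes.** Under Primary Outcome Measure, "The primary outcome is a reduction of 1 or more points of the Jawline Rating Scale (JRS" from baseline to 4 weeks after the last injection, "based on any or all of one blinded dermatologist rating, one unblinded dermatologist rating, and patient rating". No group is named. Secondary outcome 1 applies the same 1-point criterion to the patient's own rating, again with no group. Secondary outcomes 2 and 3 are the only efficacy outcomes that name the groups. Item 3 reads "Whether group 1 or group 2 has a higher reduction in the Jawline Rating Scale (JRS", and item 2 puts the same comparison to the dermatologists' ratings. Items 4 to 6 are JRS ratings by visit without groups, and items 7 to 11 are safety outcomes.

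**The regimens.** Protocol Summary and Treatment give both groups jawline filler, with preauricular (inferior cheek) filler added where needed. Group 2 also receives zygomatic cheek filler. Sixteen patients are randomised 1:1.

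**The concern.** Whether jawline treatment is enough is an absolute question. It needs the response in Group 1 judged by some standard of adequate improvement. The protocol has such a standard for the individual patient, a 1-point reduction, but never ties it to Group 1. The outcomes that do name the groups are purely relative. A higher reduction in Group 2 would not show that Group 1's treatment fell short, and similar reductions would not show that it sufficed.

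Endpoint #1 adds to the problem. As worded, it could be declared met on an all-patient figure to which Group 2 contributed most of the responders. It also allows for cheek filler as an alternative to jawline filler, a regimen that neither arm receives. The practical question that motivates the trial could then go unanswered although randomisation supplies the data.

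**Working it through.** The documents give no alpha, power, effect size, response rate or margin, so the sample size of 16 cannot be reproduced. The first check is a reading of outcomes against the question. The calculations after it are illustrations, with assumed values marked.

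**1. Outcomes against the question**

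| Outcome | 1-point criterion? | Names a group? | Gives Group 1 responder proportion? |
|---|---|---|---|
| Primary | yes | no | no |
| Secondary 1 | yes | no | no |
| Secondary 2 and 3 | no | yes | no; asks which reduction is higher |
| Secondary 4 to 6 | no | no | no |
| Secondary 7 to 11 | safety | no | no |

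**2. What an all-patient figure can tell us**

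With 16 patients at 1:1 there are 8 per arm. Exact (Clopper-Pearson) 95% limits for x responders in n are the 0.025 quantile of Beta(x, n − x + 1) and the 0.975 quantile of Beta(x + 1, n − x).

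- Assumed 12/16 overall: 75% (48% to 93%). This fits Group 1 = 4/8 (50%, 16% to 84%) with Group 2 = 8/8, and equally Group 1 = 8/8 (100%, 63% to 100%) with Group 2 = 4/8. Either split gives a two-sided Fisher p of 0.077.
- Assumed 3/8 and 8/8: 11/16 overall = 69% (41% to 89%), with Group 1 at 38% (9% to 76%).

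**3. What the group reductions can tell us**

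If reduction is summarised as a mean (the documents do not say), a mean of 0.75 in 8 patients is a total of 8 × 0.75 = 6 points. That could be six patients improving by 1 point (6/8 = 75% responders) or three improving by 2 points (3/8 = 38%). The mean does not determine the responder proportion.

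**4. What a finding of no difference can tell us**

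- Two-sided Fisher test at 0.05, 8 per arm, power by full enumeration at assumed rates: 50% v 90%, 0.22; 60% v 90%, 0.10; 70% v 90%, 0.03.
- Difference in mean JRS change detectable with 80% power at two-sided 0.05 (normal approximation): (1.96 + 0.84) × √(2/8) = 1.4 SD.
- Non-inferiority, assuming 80% response in both arms, one-sided 0.025 and 80% power: n per arm = 2 × 0.8 × 0.2 × (1.96 + 0.84)² / margin². This gives 252, 112, 63 and 28 per arm for margins of 10, 15, 20 and 30 percentage points, against 8 available.

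A null comparison at this size therefore carries almost no information on whether Group 1's regimen is enough.

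**5. What the Group 1 proportion would tell us**

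Exact 95% intervals at n = 8: 6/8 = 75% (35% to 97%); 7/8 = 88% (47% to 99.7%); 8/8 = 100% (63% to 100%). A formal rule needs a reference rate that the documents do not give. If 50% were taken as inadequate, requiring at least 7/8 has one-sided alpha (8 + 1)/256 = 0.035, with power 0.50 at a true 80% and 0.81 at a true 90%. If 30% were taken, requiring at least 6/8 has alpha 0.011 and power 0.80 at a true 80%.

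**The case against.** Several points on the other side are sound.

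- A reader might infer that the protocol has decided to pool the groups. It has not. The primary outcome names no analysis population, and the Data Analysis section gives no summaries or tests. The gap is silence.
- A reader might infer that nothing about Group 1 would emerge. Secondary outcomes 2 and 3 compare reductions from baseline, so Group 1's own reduction is a necessary by-product. What is missing is the responder proportion and any criterion for enough. Item 2 joins the groups with *and* where item 3 has *or*. Even if item 2 is read as each group against baseline, it applies no 1-point criterion.
- A reader might infer that a poor Group 1 result would stay hidden. An extreme one probably would not: 3/8 v 8/8 gives a two-sided Fisher p of 2 × 56/4368 = 0.026, and a gap that wide would probably show in the reductions too. The milder 4/8 v 8/8 split (p = 0.077) is less sure to be noticed.
- The Introduction's sentences pair jawline alone with the combined treatment, so they can be read as one comparative question, which the secondary objective and outcomes 2 and 3 do address. That covers whether adding the cheeks is better. It leaves open whether the jawline regimen suffices, which the same sentences also ask.
- Any routine report can tabulate by arm. It can, but this plan does not commit to it, and choosing between all-patient and by-arm results after seeing the data is what prespecification is meant to prevent.
- The arm definitions make the cheek wording in Endpoint #1 look like loose drafting. It may be no more than that, but it is the stated objective and it conflicts with the Purpose statement.

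**Conclusion.** The point holds as a gap in the stated outcomes and objectives, and it should be repaired. The plan poses an absolute question about Group 1 and specifies no responder summary for Group 1. At 8 per arm the planned comparison cannot stand in for one. Endpoint #1 could be declared met with Group 2 carrying the result, and its cheek alternative is untestable in this design.

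The documents do not support saying that pooling is prescribed, that a Group 1 failure would be concealed, or that any given overall rate would count as success, since no success threshold for the response rate is stated. The counts and rates in the illustrations are assumptions. Nor would the Group 1 proportion be a strict test of jawline filler alone, because that arm may also receive preauricular filler. A few pages, in the vision-loss management section and after the pain form, were not available for this check. I assume they hold no by-group efficacy outcome.

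**What to change.** 1. Report the primary responder outcome and secondary outcome 1 separately for each randomised group, with exact 95% intervals. State which rating or combination of ratings defines a primary responder, so that the count is determinate.
2. Name the Group 1 proportion as the descriptive answer on sufficiency, and label it as applying to the Group 1 regimen (jawline with optional preauricular filler).
3. Keep any all-patient figure as a summary only.
4. Reword Endpoint #1 to match the Purpose statement (jawline, or jawline plus cheek), and draw no conclusion about cheek filler by itself.
5. If more than description is wanted, fix in advance the response rate that would count as enough. Otherwise say plainly that the result is descriptive.

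The cost is a wording change and one table, with no new data or visits. The drawback is precision: per-arm intervals rest on 8 patients and span roughly 37 to 69 percentage points for 8/8 to 4/8 responders (100 − 63 and 84 − 16, allowing for rounding).

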Many practitioners also use fillers with high G prime along the jawline or lateral face to accomplish improving the jowls. This technique, alternatively called "jawline filler, jawline lift", has not received FDA approval. JUVÉDERM VOLUMA® XC injectable gel is currently FDA approved for deep injection in the cheek area to correct age-related volume loss. In practice, we have seen the advent of cheek treatments with Voluma causing noticeable lifting in the jowls and also the nasolabial fold. However, recent experimentation with filler into the mandible lateral to the jowl, sometimes accompanied by injection into the preauricular area by this author has revealed that this area has been underrepresented in filler solutions for jowling.

Protocol Summary

This study is proposed to evaluate the best protocol for achieving improvement in the sagging jawline.

JUVÉDERM VOLUMA™ XC will be injected in each of 16 women with sagging of grades 1-3 using a published jawline evaluation scale (1).

Patients will be randomized 1:1 into 2 groups:

Patient Group 1: JUVÉDERM VOLUMA™ XC 1-2 syringes (each syringe is 1 cc) will be injected bilaterally into the lateral jawline and inferior cheek area (preauricular area) (the latter area will be added if necessary to achieve visual improvement in jowl attenuation). Total syringes used per person will have a range of 1-2)

Patient Group 2: JUVÉDERM VOLUMA™ XC 1-3 syringes (each syringe is 1 cc) will be injected bilaterally into the lateral cheek (zygomatic) area plus JUVÉDERM VOLUMA™ XC 1-2 syringes (each syringe is 1 cc) will be injected into the lateral jawline and inferior cheek area (preauricular area) (the latter area will be added if necessary to achieve visual improvement in jowl attenuation). Total syringes used per person will have a range of 2-5)

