		ment	Follow	Office	Office	Follow	office	Office	medicine	medicine
			Up Call	Follow	Follow	Up Call	Follow	Follow	Video	Video Call
				Up	Up		Up	Up	Call	
			72 hours	2	4	72	8	16	6	12
			after	weeks	weeks	hours	weeks	weeks	months	months
			treat	+/- 3	+/- 3	after	+/- 3	+/- 3	after RTx	after RTx
			ment	days	days	RTx	days	days	+/- 3 days	+/- 3 days
Informed Consent	Х									
Inclusion/Exclusion										
	Х									
Medical History	X								0	
Urino Drognanov	^									
Urine Pregnancy Test	X	Х			Х					
	^	^			^					
Photography		Х		Х	Х		Х	Х		
Blinded Evaluation	Х				х		х	х		
Adverse Events		Х	Х	Х	Х	х	Х	х	X	Х
Physical Exam			Λ	Λ	, , , , , , , , , , , , , , , , , , , 		, , , , , , , , , , , , , , , , , , , 			, A
r nysicai Exam		Х		Х	Х		X	X		
Safety Eye		, A		Λ	Λ		, A	^		
Assessments		X**		Х	Х		X	X		
Cranial Nerve		 ^						 ^		
Assessments		Х		X	X		X	Х		
Patient				,	,			 		
Questionnaire/	Х			X	Х		Х	Х	X	X
Evaluation	`				``		^	^`		
Patient Pain										
Evaluation		X	X	Х	X	Х	Х	Х	Х	X
Patient Safety				- •	- •	1				
Diary***		X	X		X	Х				
Retreatment		 	,			 				
Retreatment					X*					

^{*}If requested by physician or patient and agreeable to both

^{**}Safety Eye Assessments will be performed prior to treatment and 30 minutes after treatment

^{***}Patient diary to be completed daily by email for 30 days following treatment

Voluma Jowl/Jawline Study 10001 Appendix 1: Study Schematics No Retreatment

Visit #	1	2	3	4	5	6	7	8	9
	Screening	Treat	Safety	In	In	In	In	Tele	Tele
		ment	Follow	Office	Office	office	Office	medicine	medicine
			Up Call	Follow	Follow	Follow	Follow	Video	Video
				Up	Up	Up	Up	Call	Call
			72	2	4	8	12	6	12
			hours	weeks	weeks	weeks	weeks	months	months
			+/- 4	+/- 3	+/- 3	+/- 3	+/- 3	after Tx	after Tx
			hours	days	days	days	days	+/- 3	+/- 3
								days	days
Informed Consent	X								
Inclusion/Exclusion									
	X								
Medical History									
	X								
Urine Pregnancy									
Test	X	Х							
Photography									
		Х		Χ	Х	X	Χ		
Blinded Evaluation									
	X				Х	Х	Х		
Adverse Events									
		Х	Х	Х	Х	Х	Х	Х	Х
Physical Exam									
,		Х		Χ	Х	Х	Χ		
Safety Eye									
Assessments		Χ*		Χ	Х	Х	Χ		
Cranial Nerve									
Assessments		Х		Х	Х	Х	Х		
Patient									
Questionnaire/	Х			Х	Х	Х	Х	Х	Х
Evaluation									
Patient Pain									
Evaluation		Х	Х	Х	Х	Х	Х	Х	Х
Patient Safety									
Diary**		Х	Х						
Retreatment***									

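### No baseline jowl rating separate from the qualifying Screening grade is scheduled for the patient, or specified for the MD evaluator, so the uncontrolled before/after primary outcome may include regression to the mean and qualifying inflation

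*Combined protocol and SAP*

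**What the plan says.** Patient Selection, item 1, admits women with "Jowling grade 2-3 by the Lower Face Jawline at Rest Scale (1), by both MD evaluator and patient". The Protocol Summary gives a different range: "sagging of grades 1-3 using a published jawline evaluation scale".

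Under Primary Outcome Measure, "The primary outcome is a reduction of 1 or more points of the Jawline Rating Scale (JRS", measured "at baseline versus that at 4 weeks from the last injection (whether initial or touch-up", and judged "based on any or all of one blinded dermatologist rating, one unblinded dermatologist rating, and patient rating". Secondary outcome 1 applies the same one-grade threshold to the patient's rating alone. Both randomised groups receive filler, and there is no untreated group.

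On timing, both Appendix 1 schedules mark the "Blinded Evaluation" row and the patient questionnaire row at Visit 1 (Screening), leave them blank at Visit 2 (Treatment), and resume after injection. Neither schedule has a row for the unblinded dermatologist. Data Analysis says that both dermatologists rate at baseline but does not name the visit. The rating forms carry a baseline tick-box, also without a visit.

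Photography is first marked at Visit 2. Yet item 3 of the section on scientific soundness says: "Evaluators will review individual photos without knowledge of if they are before or after photos".

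**The concern.** A grade that decides entry is a selected measurement. If part of it is rating error, a second rating of the same unchanged face tends to move back towards the population mean. A candidate who wants treatment, or an evaluator who knows the threshold, also has a reason to score at least 2. If that same grade serves as baseline, either effect can count as improvement.

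Endpoint #1 asks whether filler produces a clinically relevant improvement, and its only comparison is before versus after. Nothing in the design separates drift from filler effect. The patient's rating matters most: on the any-rater reading she alone can make herself a primary responder, and secondary outcome 1 depends entirely on her.

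The schedule also places the blinded baseline rating at a visit where no photograph is marked. It is then unclear whether that rating is live or photographic, and whether it can be masked to before/after.

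**Working it through.** The plan states no expected response rate, rating reliability, power or effect size, so there is no figure to reproduce. The check has two parts: who is exposed, and how large the drift could be.

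**1. Who is exposed**

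| Rater | Grade decides entry? | Pre-treatment rating in Appendix 1 | Separate baseline? |
|---|---|---|---|
| Patient | Yes | Visit 1 only | No |
| Blinded dermatologist | Not stated | Visit 1 only, but photographs start at Visit 2 | Unclear |
| Unblinded dermatologist | Not stated | No row | Not specified |

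The MD evaluator is not identified as either dermatologist. Whoever fills that role has no specified second baseline.

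**2. Mean drift with no true change**

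Model: rating = round(L + e), cut to 0-4. Latent severity L is Normal(m, SD 0.8) and error e is Normal(0, s), independent between ratings. Entry requires the MD and patient ratings both to be 2 or 3.

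Spurious fall = mean of (qualifying rating − later rating) among those entered.

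All parameters are assumptions, not taken from the protocol: m = 1.5 to 3.0 and s = 0.3 to 0.6 (exact repeat agreement about 67% down to 43%). Set B is a second assumption set, with latent SD 0.9 and reliability 0.6 to 0.9. Qualifying inflation adds 0.25 grade to both entry ratings. Positive values are apparent improvement.

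| Candidate mean m | Set A, no inflation | Set B, no inflation | Set B, 0.25 inflation |
|---|---|---|---|
| 1.5 | 0.09 to 0.22 | 0.08 to 0.25 | 0.31 to 0.43 |
| 2.0 | 0.05 to 0.11 | 0.04 to 0.13 | 0.27 to 0.32 |
| 2.5 | about 0 | 0.00 to 0.02 | 0.20 to 0.23 |
| 3.0 | −0.05 to −0.10 | −0.04 to −0.10 | 0.08 to 0.19 |

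Set A with the same inflation gives about 0.09 to 0.41 across all four means. A rater whose grade did not decide entry shows 0.00. With an independent second pre-treatment rating as baseline, every rater shows 0.00 in every scenario.

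**3. The other entry range**

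With a 1-3 window, as in the Protocol Summary, the drift at m = 1.5 falls to 0.03-0.07 (set A) or 0.03-0.09 (set B). At m = 2.0 it is zero.

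**4. Responders with no true change**

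- One deciding rater, m = 1.5, set A: a fall of at least one grade in 19-36% from the qualifying grade, against 16-29% from a separate baseline. The excess is 19 − 16 = 3 to 36 − 29 = 7 points, or 16 × 0.03 = 0.5 to 16 × 0.07 = 1.1 patients.
- Any of three raters, set A, qualifying versus separate baseline: 43-69% vs 41-64% at m = 1.5; 41-65% vs 41-64% at 2.0; 38-61% vs 41-64% at 2.5.
- Any of three raters with 0.25 inflation, set B, reliability 0.75: 74%, 71%, 67% and 63% at m = 1.5, 2.0, 2.5 and 3.0, against 60% with a separate baseline. The excesses of 14, 11, 7 and 3 points are 16 × 0.14 = 2.2, 1.8, 1.1 and 0.5 patients.
- At that 60% background rate, 16 × 0.60 = 9.6 patients respond on average, and the chance of at least 8 of 16 is 0.86.

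**The case against.** A reader might infer that the primary outcome certainly contains drift in favour of filler, for every rater. The documents do not support that.

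- Entry is a two-sided window, so the direction depends on a candidate mean that is never given. The wider range in the Protocol Summary, the 35-65 age limits and the exclusion of obesity make a pool centred near 2 plausible, but this is inference.
- Being rated at the eligibility visit is not enough. Only a rater whose grade decides entry regresses. The unblinded dermatologist's baseline visit is unspecified; it is not shown to be Screening.
- The blinded rater may already be protected. Masked rating of individual photographs is promised, and VISIA photographs are taken before treatment. What remains is a conflict with the schedule. The line on pre-treatment photographs at enrolment does not settle which image a Visit 1 rating would use.
- Without inflation, most false responses come from rating noise and the any-of-three rule. A separate baseline barely changes the any-rater rate at a mean of 2.0, and raises it slightly at 2.5.
- Qualifying inflation is plausible, but nothing in the protocol sizes it.

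A reader might also infer that the comparison of jawline alone with jawline plus cheek is biased. It is randomised, and this mechanism acts on both groups alike in expectation.

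All these limits stand. They do not remove the structural gap: the patient's qualifying grade is her only scheduled pre-treatment grade, and no passage available defines another baseline.

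**Conclusion.** The point holds as a possibility, not a certainty. Followed as scheduled, the patient's entry grade is also her baseline, and the MD evaluator has no specified separate baseline. The uncontrolled primary outcome and secondary outcome 1 may therefore include regression to the mean and qualifying inflation. Under the assumptions above, regression alone ranges from roughly a fifth to a quarter of a grade in favour of treatment to a tenth of a grade against it. With 0.25-grade inflation it favours treatment in every scenario tested.

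Two conflicts must be reconciled whatever the size of the bias: the entry grade (Protocol Summary versus Patient Selection), and the visit and image that supply the blinded baseline (Appendix 1 versus the masked photograph rating).

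The change is worth making because it is cheap and removes the drift in expectation, provided the second rating is independent of the first. It would not by itself make the any-rater responder rate interpretable.

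**What to change.** Use Screening grades for eligibility only. Define baseline for every JRS outcome as a Visit 2 rating made before injection:

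- The blinded dermatologist rates the pre-treatment VISIA photographs already planned at Visit 2, in random order with the follow-up photographs.
- The patient and the unblinded dermatologist repeat the 0-4 grade before injection, without sight of the Screening grade.
- All enrolled patients stay in the analysis whatever their Visit 2 grade.

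In both Appendix 1 schedules, move the baseline blinded rating to Visit 2, mark the patient's repeat grade there, and add a row for the unblinded dermatologist. State who the MD evaluator is, and reconcile the two entry ranges.

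The cost is two brief ratings at an existing visit, with no new photographs, raters or visits. A few baseline grades may fall outside 2-3. Patients may recall their Screening score, in which case the second rating is not fully independent and some drift remains. The rule for combining the three raters needs its own correction.
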